1. INTRODUCTION & PURPOSE

This document details the rules proposed and the presentation that will be followed, as closely as possible, when analysing and reporting the main results from the STAR Trial.

The purpose of the plan is to:

- Ensure that the analysis is appropriate for the aims of the trial, reflects good statistical practice, and that interpretation of a priori and post hoc analyses respectively is appropriate.
- 2. Explain in detail how the data will be handled and analysed to enable others to perform the actual analysis in the event of sickness or other absence.
- 3. Protect the project by helping it keep to timelines and within scope.

Additional exploratory or auxiliary analyses of data not specified in the protocol are permitted but fall outside the scope of this analysis plan (although such analyses would be expected to follow Good Statistical Practice).

The analysis strategy will be made available if required by journal editors or referees when the main papers are submitted for publication. Additional analyses suggested by reviewers or editors will, if considered appropriate, be performed in accordance with the Analysis Plan, but if reported the source of such a post-hoc analysis will be declared.

Editorial changes

Amendments to the statistical analysis plan will be described and justified in the final report of the trial in **Table 51** of this document.

Tables and figures

Throughout this document references are made to any skeleton tables and figures to be used in the reporting of the trial (e.g. **Figure F1** or **Table T1**). Such tables and figures can be found in **Appendix A** of this document and are intended as a guide for trial reporting. Final versions of the tables/figures may differ, tables may be combined, and/or their layout or numbering may evolve. However, the content will be consistent with **Appendix A**.

In this document, references to the protocol refer to "version 9, 04-02-2019".

2. TRIAL BACKGROUND AND OBJECTIVES

2.1. Background

Please refer to the trial protocol, section titled "Background".

2.2. Trial objectives and aims

Please refer to the trial protocol, section titled "Aims and Objectives".

3. TRIAL DESIGN AND PROCEDURES

3.1. Trial design and configuration

Please refer to the trial protocol, section titled "Overview of trial design", in the subsection titled "Main trial".

3.2. Trial centres

Please refer to the trial protocol, section titles "Patient selection and recruitment".

3.3. Selection criteria

Please refer to the trial protocol, section titled "Selection criteria".

3.4. Description of interventions

Please refer to the trial protocol, section titled "Intervention: STAR Care Pathway".

3.5. Control: Care as usual

Please refer to the trial protocol, section titled "Control: Usual Care".

3.6. Randomisation procedures

After patients have provided written, informed consent to participate and have completed and returned a baseline questionnaire, they will be randomly allocated to the STAR pathway or usual care. Randomisation will occur as soon as possible after the baseline questionnaire is received by the research team. Randomisation with allocation concealment will be conducted remotely via the Bristol Randomised Trials Collaboration using a web-based randomisation system. Randomisation will take place on a 2:1 basis to ensure that the intervention service is running at sufficient capacity to enable a pragmatic assessment of its effectiveness and, particularly, cost-effectiveness. If the intervention is operating to a sufficient degree of capacity per-protocol and CACE analyses will be more reliable and have higher power. To ensure reasonable balance between the two treatment groups, allocation will be minimised by pain in the replaced knee (assessed with both the Brief Pain Inventory Severity and the Brief Pain Inventory Interference Scales – these scores are both categorised using tertiles of STAR PACE data for these scores) and stratified by orthopaedic centre. Randomisation will be performed by a member of the research team at the co-ordinating centre and the local researcher at each site will then inform participants of the result.

3.7. Sample size and justification

We estimate that 20% of patients who have had primary total knee replacement will have long-term post-surgical pain. Based on our recent trial in total knee replacement (Wylde V, 2015), we estimate conservatively that we will achieve a recruitment rate of 40% (an 8% conversion rate for number randomised out of those screened). Surgical audit data show that the four trial centres conduct over 1,900 primary total knee replacement procedures annually. Over 30 months, this equates to 4,750 procedures, and we estimate that 950 of these patients will have long-term post-surgical pain. With a recruitment rate of 40% we can recruit 380 patients over this period. In our recent trial we achieved 83% follow-up (Wylde et al, 2015); therefore, allowing for a generous 25% loss to follow-up in the STAR trial, a total of 380 participants randomised would yield 285 for analysis. For a 2:1 intervention:control randomisation ratio we would have a power of 80% to 90% to detect standardised differences of between 0.35 to 0.40 standard deviations (SDs) using a 2-sided 5% significance level. From previous studies (Dworkin RH, 2008), (Bruce J, 2014), the SDs for each of the BPI Interference and Pain Severity scales for patients with long-term postsurgical pain has been observed to be approximately 2, in which case the target effect size translates to a difference between intervention and control groups of between 0.7 and 0.8 scale points for both scales. Such a difference would be worthwhile detecting clinically, since the current consensus statement indicates that differences of approximately one scale point can be deemed the minimally important difference for both of these scales (Bruce J, 2014),(Kroenke K, 2009).

3.8. Blinding and breaking of blind

Please refer to the trial protocol, section titled "Blinding".

3.9. Trial committees

Please refer to the trial protocol, section titled "Trial organisation and oversight".

3.10. Outcome measures

Please refer to the trial protocol, section titled "Outcome measures".

4. GENERAL ANALYSIS CONSIDERATIONS

4.1. Analysis populations

The primary analysis of the data will be on a complete case basis, in accordance as far as possible with the intention to treat (ITT) principle whereby we analyse as randomised, disregarding protocol deviations or non-compliance. Sensitivity analyses will utilise imputation methods to handle missing data to ascertain whether their exclusion in the primary analysis has had any effect within an ITT paradigm. In addition, a crude per protocol analysis will be performed using those patients who adhered with the intervention sufficiently. Adherence to the intervention, for a patient in the intervention arm, is defined as the patient attending their assessment clinic appointment and for patients in the control arm, adherence cannot be measured as they adhere by using usual care. We assume that all patients in the control arm have adhered to the intervention allocation. This per protocol analysis will address the same points as the comparison based on groups as allocated (hereafter referred to as 'the ITT analysis') just using a different population. Since these results are likely to be biased, we will also use the Complier Average Causal Effect (CACE) approach to adjust for any selection effects in terms of adherence.

4.2. Derived variables

Co-primary outcome measures

The Brief Pain Inventory is a questionnaire which consists of 14 questions. Eleven of which are included in Section A of the follow-up questionnaire for STAR. The two scores which will be used as our co-primary are described below.

- Pain Severity Score: The Pain Severity Score is calculated by taking the mean of the rating scores of the first four questions in Section A of the questionnaire (Q1+Q2+Q3+Q4)/4.
- Pain Interference Score: The Pain Interference Score is calculated by taking the mean of the last seven questions in Section A of the questionnaire (Q7+Q8+Q9+Q10+Q11+Q12+Q13)/7.

Secondary outcome measures

• Oxford Knee Score (OKS)

The OKS is calculated using the items in section B of the questionnaire. To calculate the OKS, we sum the responses to the 12 items (individual items scored 0-4, worst to best). The total score has a range of 0-48 (worst to best). The Oxford Knee Score can be split into two subscales: the pain and function subscales.

- OKS Pain subscale: the raw subscale is equal to the sum of the responses to the following questions: 1, 4, 5, 6, 8, 9 and 10. This is then standardised to range from 0 to 100 by multiplying by 3.57.
- OKS Function subscale: the raw subscale is equal to the sum of the responses to the following questions: 2, 3, 7, 11 and 12. This is then standardised to range from 0 to 100 by multiplying by 5.
- PainDETECT

The PainDETECT score is calculated using items in Section C of the questionnaire. The first seven questions are scored zero to five (Never – Very Strong). The eighth question is a picture representation of the pain and these are scored between negative one and positive one. Lastly the ninth question is scored 2 if "Yes" is selected and zero if "No" is selected. The sum of each score provides the PainDETECT score. This ranges from -1 to 38 and scores fall into three categories: (-1 to 12) nociceptive, (13-18) unclear and (19-38) neuropathic pain.

• DN-4

The DN-4 score is a score out of 7 corresponding to the number of 'yes' answers the patient gave in Section D.

• EQ-5D-5L

The EQ-5D-5L provides a state of 5 characters 'XXXXX'. Each of the five items in Section E provide an element of the state from 1 to 5. The best-case scenario is 11111 which would mean there is no problem with each area. The worst-case scenario is 55555 and this indicates that there are high levels of concern with all five areas (mobility, self-care, usual activities, pain/discomfort and anxiety/depression). The EQ-5D-5L will be used by the Health economics team and will not be used for Statistical analysis.

• Short Form-12

This outcome is derived by software using responses from Section F of the questionnaire. The statistician will process the data in the software to give a score which will be in the desired format to be analysed.

• Hospital Anxiety and Depression Scale (HADS)

HADS is split into two sub-scales, the Anxiety Scale and the Depression Scale. Each scale comprises of the sum of responses from 7 items from Section H of the questionnaire. Each item is scored from 0 to 3 with 0 being the best-case scenario and 3 being the worst. Each of the two sub-scales are categorised into a normal score (0-7); borderline anxiety/depression (8-10) and clinical anxiety/depression (≥11).

• ICECAP-A

ICECAP-A uses responses from Section I of the questionnaire and provides a state of 5 characters 'XXXXX'. This then allows us to calculate a tariff value for items which make up the state. This tariff value is the sum of pre-specified values corresponding to the answers given in the questionnaire. The code for this is presented in the appendix.

• Pain Catastrophizing Scale

The Pain Catastrophizing Scale is split into three sub-scales, The Rumination Scale, The Magnification Scale and The Helplessness Scale. Each scale is a sum of the ratings given to each of sthe following items of Section J of the questionnaire:

- 1. The Rumination Scale: 8, 9, 10, 11
- 2. The Magnification Scale: 6, 7, 13
- 3. The Helplessness Scale: 1, 2, 3, 4, 5, 12

The whole scale is additive of the three subscales and will be used for primary analysis however we will also explore analysis of the individual sub scales.

• Pain Solutions Questionnaire

The Pain Solution Questionnaire is split into four sub-scales, Solving Pain, Meaningfulness of Life despite Pain, Acceptance of Insolubility of Pain and Belief in Solution. Each scale is a sum of the answers given to each of the following items of Section K of the questionnaire:

- 1. Solving Pain: 7, 10, 11, 12
- 2. Meaningfulness of Life despite Pain: 1, 2, 3, 8, 13

- 3. Acceptance of Insolubility of Pain: 4, 5, 9
- 4. Belief in Solution: 6, 14

The four sub scales will be analysed separately.

• Self-Administered Patient Satisfaction Scale for Primary Hip and Knee Arthroplasty The satisfaction scale is made up of the first four questions of Section L. Items are scored on a 4-point Likert scale with response categories consisting of very satisfied (100 points), somewhat satisfied (75 points), somewhat dissatisfied (50 points), and very dissatisfied (25 points). The scale is calculated by taking an unweighted average over these four questions providing a score ranging from 25 to 100 (with 100 being most satisfied). This will be treated as a continuous variable in analysis.

• Body Map

The body map in Section M of the questionnaire is used to determine chronic widespread pain according to Manchester's definition CWP(M). Patients indicate sections of the body where they feel pain by shading in sections of a mannequin (viewed from front, back, left and right) and the Manchester definition is used to categorise patients into those who have CWP(M) and those who do not. To satisfy the Manchester definition of chronic widespread pain [CWP(M)], pain must be reported in at least two sections of each two contralateral limbs and in the axial skeleton and have been present for at least 3 months. Although the presence of pain at 3 months is not recorded in the trial, we will classify patients based on the other elements of the definition.

• Free text comment box

The free text comments at the end of each questionnaire will be analysed thematically by the qualitative team and will not be used for statistical analysis other than to inform responses to other sections of the questionnaire.

4.3 Procedures for missing data

In all tables missing data will be indicated by footnotes. If the amount of missing data differs substantially between treatment groups potential reasons will be explored. Sensitivity

analyses will be conducted (including the use of multiple imputation by chained equations (mice) methods) to examine the influence of missing data on the key trial findings. When using mice, 25 datasets will be generated and 10 switching procedures undertaken. The imputation model will include all variables predictive of missingness, together with all of the variables included in the main substantive model. Comparisons of results from ITT analyses of complete cases with ITT analyses where missing data were imputed will be presented in **Table 17 - Table 29**.

The model used for imputation will include a baseline measure of the outcome, any other observations of the outcome at different follow-up times, randomisation group, age/gender, centre and any other restriction variables for the randomisation (i.e. stratification/minimisation), we will consider also including any other variables that are either strongly associated with missingness or likely to have some prognostic value. This list will be finalised before conducting the mice analyses.

In the event of missing data, we will follow guidelines where applicable and use mice to impute scores if the missingness exceeds the guidelines.

BPI (severity and interference): The first four items of section A must be complete to calculate the score for the severity scale. Four of the last seven items of section A of the questionnaire must be complete to calculate the interference scale by averaging complete items.

OKS: If 1 or 2 questions are missing, then the mean value can be used to fill the gaps.

PainDETECT: If any of the first seven items of section C are missing impute with the mean of the complete items in the first seven items. If question 8 of section C is missing do not add or subtract anything from the score (ie. Treat the value of that item as zero). If question 9 is missing, assume the response is no, thus, treat the value of the item as zero.

DN-4: No score can be calculated if more than 4 items are missing. The score is a proportion of "Yes" responses.

Short form-12: The short form-12 requires 50% of items to be completed.

HADS: The score for a single missing item from a sub scale is inferred by using the mean of the remaining six items. If more than one item is missing from a sub scale, that sub-scale cannot be calculated.

ICECAP-A: There is not any internal way of dealing with missing data, as each attribute on the questionnaire is intended to be mutually exclusive. For this trial we will fill the missing value with the mean of the completed items if one item is missing. If two or more items are missing, we will impute the whole score using mice.

Pain Catastrophizing Scale: There are no formal guidelines for dealing with missing data in the PCS. We allow one item to be missing from each subscale and this item will be replaced by the mean of the complete items in that subscale. If more than one item is missing from each subscale, we will impute the whole score using mice.

Pain Solution Score: 75% of items in each subscale need to be complete in order to calculate a score. We extrapolate the score to new total sub-scores. For example, if 4 items of 5 have been completed. The total score of the 4 is divided be 4 and multiplied by 5.

Satisfaction scale: There are no formal guidelines for dealing with missing data. If one item is missing, we will fill the missing value with the mean of the completed items. If more than one item is missing, we will impute the whole score using mice.

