7.3. Primary analysis

The primary and main secondary analyses will be conducted using the ITT principle (that is, comparisons of groups as allocated) using the appropriate regression model. Assumptions for each regression will be checked to make sure the correct method of analysis is being used.

Each of the co-primary outcome measures, BPI Severity and BPI Interference scales, will be analysed to compare treatment groups using linear regression. The models will be adjusted for trial centre as a fixed effect and baseline BPI pain scores. Estimates will be calculated of the effect that intervention has on each of the BPI scores compared with usual care. Primary analysis will be adjusted for variables which are imbalanced at baseline to see if this makes a marked difference to the unadjusted primary analysis.

Results from the primary analysis will be presented in **Table 14**.

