7.7.2 Subgroup analysis

Subgroup analyses on the primary outcomes will be performed by introducing appropriate interaction terms between the intervention group and other patient characteristics in the regression models, to investigate any differential effects in certain subgroups of the population. These factors will be trial centre and baseline Oxford Knee Score. The OKS will be treated as a continuous variable ranging 0-48; however, for descriptive purposes we will consider the conventional categories of: 0-19 (severe knee arthritis); 20-19 (moderate to severe knee arthritis); 30-39 (moderate knee arthritis) and 40-48 (satisfactory joint function).

Another subgroup analysis will be performed for those sites who limit patients who are less than 1 hour drive away versus those who accept all patients regardless of the distance from site.

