The Pain Solution (PaSol) Questionnaire measures two opposing modes of coping with pain. First, 'assimilative coping' captures the style in which patients increase effort and tenaciously pursue their goal of pain control. Patients scoring high on the 'solving pain' subscale and low on the 'meaningful life despite pain' and 'acceptance of the insolubility of pain' sub-scales are high in assimilative pain coping. Second, 'accommodative coping' captures the style in which patients accept that there is unlikely to be a cure for pain and a switch in goals to living with pain is a sensible next step. Patients scoring low on the 'solving pain' subscale and high on the 'meaningful life despite pain' and 'acceptance of the insolubility of pain' sub-scales are high in assimilative pain coping. There is a strong possibility that those with different coping profiles will respond differently to intervention. Subgroup analyses will be performed using baseline PASOL data to investigate differential effects on outcomes through the use of the relevant interaction terms in regression models. First a (continuous) composite score on a single dimension of accommodative to assimilative scale will be created using an established algorithm (Geert Crombez, 2008) based on simple summation of scores accounting for their logical direction(s). Second, a three-category scale will be produced as follows: a) high in assimilative and low in accommodative; b) no clear preference; c) low in assimilative and high in accommodative. The exact determination of the thresholds inherent in the categorical version will be influenced both by the category labels of the underlying items/scores and their frequencies – for example, both taking into consideration any clear modality in the frequency distribution and so that none of the above three categories are either too large or too small to be of value in the analysis. It is emphasised, though, that the categorisation will be determined in advance of the regression models considering the relevant interactions, and that the primary subgroup analyses for this measure will be for the continuous version of the underlying variable.

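### SAP 4.3 as written implies a pooled additive imputation model; imputing within each arm, with baseline PaSol and OKS named, would make the mice check more trustworthy

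*SAP*

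**What the plan says.** The primary analysis is complete-case. SAP 4.1 gives the imputed analysis its purpose: "to ascertain whether their exclusion in the primary analysis has had any effect within an ITT paradigm".

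SAP 4.3 sets the content of the imputation model. The general rule is: "The imputation model will include all variables predictive of missingness, together with all of the variables included in the main substantive model". The specific list is a baseline measure of the outcome, "any other observations of the outcome at different follow-up times, randomisation group, age/gender, centre", and the other stratification or minimisation variables. Further variables may be considered, and "This list will be finalised before conducting the mice analyses". There are to be 25 datasets and 10 cycles. Results go beside the complete-case and best- and worst-case rows in Tables 17-29.

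The main model has main effects only (SAP 7.3): "The models will be adjusted for trial centre as a fixed effect and baseline BPI pain scores".

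SAP 7.7.2 plans allocation interactions with trial centre and baseline OKS, "to investigate any differential effects in certain subgroups of the population". On the pain-coping questionnaire (PaSol) it adds: "There is a strong possibility that those with different coping profiles will respond differently to intervention".

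**The concern.** Nothing in 4.3 mentions imputation by arm or an interaction with allocation, and the general rule ties the imputation model to a main-effects model. Read naturally, that is one additive model for both arms. The slope of the 12-month score on baseline, on the 6-month score and on any auxiliary variable is then common to the two arms.

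A variable that modifies the treatment effect has, by definition, different slopes in the two arms. If it also predicts loss, the additive model gives the missing patients the treatment difference seen among the observed ones. The mice row can then sit close to the complete-case row with both wrong in the same direction, and a reader would conclude that the exclusions did not matter. Adding more main effects does not help, because the missing term is the interaction with allocation.

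**Working it through.** **Planning figures (SAP 3.7).** 380 × 0.75 = 285 analysed. At 2:1 that is 190:95, with power 79.5% at 0.35 SD and 88.9% at 0.40 SD, in line with the stated 80% to 90%. At 2:1, 380 randomised is about 253:127, and 127 × 0.75 ≈ 95 observed control outcomes. With SD 2 the target is 0.7-0.8 points. The SAP gives no figure for the imputation itself, so every slope and odds ratio below is an assumption.

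**Mechanism.** Let z be a standardised predictor with effect δ + γz, so the average effect is δ. Let loss follow logit p = a + βz in both arms, and let m be the mean of z among those observed: m = ∫z(1−p)φ dz / ∫(1−p)φ dz. An additive model fitted to observed patients estimates a difference of δ + γm and gives the same difference to those imputed. The bias is therefore about γm in both the complete-case and the pooled row. For a predictor with SD 2 whose slopes differ by Δs between arms, γ = 2Δs.

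Values of m by numerical integration: −0.159 (odds ratio 2 per SD, 25% loss), −0.228 (odds ratio 3, 25% loss), −0.228 (β = 1, 27% loss), −0.122 (β = 0.5, 26% loss).

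**Simulation against the formula.** 253:127 randomised and outcome SD about 2 throughout. Rows 1-4: loss depends on the 6-month score, 25% loss, true effect −0.75, 1,200 trials, 25 imputations. Rows 5-7: a baseline modifier drives loss, no 6-month score in the model, true effect −0.70, 1,500 trials, 5 imputations, Monte Carlo SE about 0.006. Entries are bias in points.

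| Assumption | γm | Complete case | Pooled mice | Mice by arm |
|---|---|---|---|---|
| 1. 6-to-12-month slopes 0.7 control / 0.7 intervention | 0 | about 0 | about 0 | about 0 |
| 2. 0.8 / 0.6, OR 2 | −0.4 × −0.159 = 0.064 | 0.068 | 0.072 | 0.008 |
| 3. 0.8 / 0.4, OR 2 | −0.8 × −0.159 = 0.127 | 0.128 | 0.129 | 0.003 |
| 4. 0.8 / 0.4, OR 3 | −0.8 × −0.228 = 0.182 | 0.187 | 0.183 | 0.000 |
| 5. Modifier 0.35 per SD, β = 1 | 0.35 × −0.228 = −0.080 | −0.08 | −0.08 | 0.00 |
| 6. Modifier 0.70 per SD, β = 1 | 0.70 × −0.228 = −0.160 | −0.16 | −0.16 | 0.00 |
| 7. Modifier 0.35 per SD, β = 0.5 | 0.35 × −0.122 = −0.043 | −0.04 | −0.03 | 0.01 |

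In row 4, 95% CI coverage is 88% pooled and 95% by arm. A milder case, slopes 0.8 / 0.7 with odds ratio 2, leaves about 0.02 points.

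**Effect of the listed 6-month score.** When that score is fully observed and reflects the same baseline modifier, the pooled bias in rows 5 and 6 falls to −0.03 and −0.07, against −0.07 and −0.16 in complete cases. By arm it is 0.01 and 0.00. The carried-over bias is thus roughly halved. There is no such protection when the 6-month score is missing too, nor when its own slope differs by arm (rows 2-4).

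**By-arm imputation without the modifier.** With a coping score modifying the effect by 0.3 per SD and odds ratio 2 for loss, by-arm imputation that omits the score leaves −0.044, against −0.043 for a pooled model that includes it (no 6-month score). With the 6-month score the figures are −0.016 and −0.019. Splitting by arm therefore cures this case only if the score is in the model.

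**Precision.** The SD of the estimate was 0.218-0.230 pooled and 0.220-0.236 by arm, about 0-3% larger.

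**The case against.** - **The text is silent on functional form.** 4.3 lists variables, neither requires nor rules out by-arm imputation, and leaves the list open. This stands: a reader might infer that the plan forces equal slopes, and it does not say so. The open clause concerns which variables to add, however, and a main-effects model is the natural default given the tie to 7.3.
- **Mice is not the only missing-at-random analysis.** This also stands. The repeated-measures model in 7.6.4 uses every patient with at least one follow-up score, and best- and worst-case rows are planned too. But 7.6.4 has no arm-specific slopes, drops patients with neither follow-up, and focuses on the allocation-by-time p-value. It does not replace the mice row.
- **The plan does not expect heterogeneity.** It calls it a strong possibility for coping profile and declares subgroup work low-powered (7.7). That limits what may be claimed about likelihood. The bias itself does not depend on whether an interaction test has power.
- **Bias needs a second condition.** Nothing in the SAP says that coping, OKS or centre predicts loss. The 25% loss is described as generous, beside 83% follow-up in an earlier trial. At 17% loss, m is −0.110 for odds ratio 2, so slopes 0.8 / 0.6 give 0.4 × 0.110 = 0.044 points.
- **Only a sensitivity row is touched.** Correct: the primary estimate is unchanged.

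**Conclusion.** The point holds as an inexpensive improvement to the missing-data check. It does not show an error in the primary analysis. As written, 4.3 implies a pooled additive model. Where a variable has arm-specific slopes and also predicts loss, that model carries over part or nearly all of the complete-case bias. Over the assumed range this is about 0.02 to 0.18 points, or 0.02/0.8 = 2.5% to 0.18/0.7 = 26% of the target difference, against an SD of the estimate of about 0.22. The upper end needs the 6-to-12-month slope to halve between arms together with an odds ratio of 3 for loss. With equal slopes there is no bias.

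A reader might infer that the mice row will simply repeat the complete-case row. The documents do not support that. It is the limiting case, and for a baseline modifier an observed 6-month score, which the plan lists, moves the mice row about halfway back to the truth.

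**What to change.** In SAP 4.3, state that imputation is run separately within each randomised group (Stata: `mi impute chained` with `by(allocation)`). Keep the listed variables, 25 datasets and 10 cycles, and add baseline PaSol and baseline OKS by name. Then combine the arms and fit the planned analysis model for Tables 17-29. Using the continuous PaSol composite from 7.7.2 would keep that addition to one term. If a sparse binary outcome (Table 29) does not converge by arm, use named interactions with allocation instead.

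The cost is a sentence or two of SAP text, one command option, about 0-3% more SD in the imputed estimate, and a smaller control-arm model. That arm has about 95 observed outcomes. The simulation used 11 predictors, or 95/11 ≈ 9 observed control outcomes per predictor, so the list of further auxiliary variables should stay short.

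### The PainDETECT missing-item rule sets no minimum, so a score can rest on one of the first seven items and still count as observed

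*SAP*

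**What the plan says.** SAP section 4.2 builds PainDETECT from nine questions: seven graded items scored 0 to 5, a picture question for which "these are scored between negative one and positive one", and a ninth question worth 2 for Yes and 0 for No. It describes the total as follows: "This ranges from -1 to 38 and scores fall into three categories: (-1 to 12) nociceptive, (13-18) unclear and (19-38) neuropathic pain".

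Section 4.3 then deals with gaps in three ways:

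- Items 1 to 7: "If any of the first seven items of section C are missing impute with the mean of the complete items in the first seven items".
- Question 8: "If question 8 of section C is missing do not add or subtract anything from the score".
- Question 9: "If question 9 is missing, assume the response is no, thus, treat the value of the item as zero".

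No minimum number of answered items is attached to any of these. Section 4.3 also has a general fallback to multiple imputation (mice) for scores whose missingness goes beyond the instrument's guideline. PainDETECT has no stated limit to go beyond.

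The other scales do have one. For a HADS subscale, for instance, "If more than one item is missing from a sub scale, that sub-scale cannot be calculated". BPI interference needs four of its seven items.

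**The concern.** As written, the rule scores a PainDETECT form as long as any one of the first seven items has been answered. Only a form with none of the seven lacks a score. A score that rests on one answer is not marked as weak. It enters the complete-case analysis as observed, and it is treated the same way in every row of Table 21 (complete case, best case, worst case, mice). The sensitivity analysis meant to show the influence of missing data therefore cannot reveal it. Tables 5 to 8, which count the questionnaires usable for each score, would also show PainDETECT completion on a looser standard than the other scales.

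The question 9 rule is a smaller, separate matter. Treating silence as No moves the score in one direction only.

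What is at stake is the precision and credibility of one secondary outcome. The co-primary BPI scores have their own limits and are not affected.

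**Working it through.** **1. Scale range (the plan's own figure).** From the item scoring in section 4.2:

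- Minimum: 7 × 0 + (-1) + 0 = -1.
- Maximum: 7 × 5 + 1 + 2 = 38.

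This reproduces the stated range.

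**2. Limits in section 4.3, side by side.**

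| Score | Limit stated |
|---|---|
| BPI severity | all 4 items |
| BPI interference | at least 4 of 7 |
| OKS | at most 2 missing |
| DN-4 | at most 4 missing |
| SF-12 | 50% of items |
| HADS, per subscale | at most 1 missing |
| ICECAP-A | at most 1 missing |
| Pain Catastrophizing, per subscale | at most 1 missing |
| Pain Solution, per subscale | 75% of items |
| Satisfaction | at most 1 missing |
| PainDETECT | none |

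**3. One answered item, exact bounds.** Let the single answer be x, with questions 8 and 9 blank. The rule gives 7x. The true total lies between x - 1 (six unseen items at 0, question 8 at -1, question 9 No) and x + 30 + 1 + 2 = x + 33. The error therefore lies between 6x - 33 and 6x + 1.

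| x | Score 7x | True total | Error |
|---|---|---|---|
| 0 | 0 | -1 to 33 | -33 to +1 |
| 1 | 7 | 0 to 34 | -27 to +7 |
| 2 | 14 | 1 to 35 | -21 to +13 |
| 3 | 21 | 2 to 36 | -15 to +19 |
| 4 | 28 | 3 to 37 | -9 to +25 |
| 5 | 35 | 4 to 38 | -3 to +31 |

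A one-point change in that answer moves the total by 7. No distributional assumption is needed for this table.

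**4. Typical error, under assumptions.** The SAP gives no item statistics. The simulation used 400,000 patients and seven exchangeable items, rounded and truncated to 0-5 from a normal with mean 2 and SD 1.5. Inter-item correlation was 0.2, 0.4 or 0.6; the probability of Yes to question 9 was 0.2, 0.5 or 0.8; the four pictures of question 8 were equally likely. Questions 8 and 9 were left blank and scored 0.

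| Items answered | SD of error in total |
|---|---|
| 1 | 6.1 to 8.2 |
| 2 | 4.0 to 5.4 |
| 4 | 2.4 to 3.2 |
| 6 | 1.5 to 1.9 |

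The SD of the true total in these settings was 5.5 to 7.8, so the error from one item is about as large as the spread between patients.

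The gain from a limit depends little on the assumptions. For exchangeable items with SD σ and correlation ρ, the variance of the mean-fill error from k answered items is σ²(1 - ρ) × 7(7 - k)/k. For k = 1 the last factor is 42 and for k = 4 it is 5.25. The ratio of SDs is √(42/5.25) = √8 = 2.83, whatever σ and ρ. The simulated mean-fill SDs agree: 8.11/2.87 = 2.83 at ρ = 0.2 and 5.95/2.10 = 2.83 at ρ = 0.6.

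**5. Direction of the mean-fill.** With exchangeable items missing at random, the average mean-fill error was about 0 in every setting. If patients skip symptoms they do not have, it is upward: one item scored 3 and six skipped items whose true value is 0 give 7 × 3 = 21 against a true item sum of 3.

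**6. Question 9.** The error is 0 if the true answer is No and -2 if it is Yes. Its average is -2 × P(Yes), for example -0.2 at 10% Yes and -1.8 at 90%. A blank question 8 scored 0 can be wrong by 1 point either way.

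**The case against.** Several points on the other side stand.

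- **Frequency.** One answer out of seven is the extreme case. Under SAP section 6.2, blinded assessors telephone patients to complete missing items, so near-empty forms should be uncommon. With six items answered the error is small.
- **Comparison between arms.** The same rule applies to both arms. A shift in level common to both does not by itself bias the difference in means. That would need missingness, or the true answers behind it, to differ by arm, and section 4.3 promises to explore reasons if missing data differ substantially between groups.
- **Source of the rule.** Section 4.3 says where formal guidance is lacking for the Pain Catastrophizing and satisfaction scales and says nothing of the kind for PainDETECT, so the rule may come from an instrument guideline. This cannot be checked from the SAP, and it would not supply the missing limit.
- **Appendix code.** The PainDETECT code in the appendix is a plain sum, which in Stata gives missing when any item is missing. The BPI interference code is also a plain sum, so the code does not carry out the section 4.3 rules for either scale and does not show that partial PainDETECT forms would go unscored.

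Two stronger readings are tempting. A reader might infer that PainDETECT scores are biased low overall. The documents support a fixed downward direction only for question 9, by 0 to 2 points; the mean-fill can err either way. A reader might also infer that patients will be put in the wrong pain category in the results. Section 4.2 lists the categories, but Table 13 has PainDETECT as a continuous outcome under linear regression, and no planned table or model uses the cut-points.

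None of this removes the gap: the rule as stated accepts one answer as a full score.

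**Conclusion.** The point holds as a defect in a stated scoring rule for one secondary outcome. Section 4.3 lets one answered item stand for seven, out of line with every other multi-item score given a rule there, and the resulting score is never passed to mice. The possible error from one item with questions 8 and 9 blank is -33 to +31 points, by arithmetic alone. The error SDs in step 4 of the working rest on assumed item distributions and correlations; the factor of 2.83 between one and four items needs only exchangeable items. The expected effect is mainly noise.

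The question 9 rule is a separate, bounded understatement of at most 2 points for a patient whose true answer is Yes. The effect on the trial's PainDETECT comparison cannot be sized, because the SAP gives no frequency of partly completed forms. It is probably small. This is a cheap improvement and does not threaten the main conclusions.

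**What to change.** In SAP section 4.3:

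- State a minimum number of answered items among the first seven before a PainDETECT score is formed. Four of seven, as for BPI interference, is one choice already used in the plan. Other limits would serve, and the choice should be fixed before analysis.
- Below that minimum, set the score to missing and impute it with mice in the sensitivity analysis.
- Keep forms whose only gap is question 9. Discarding an otherwise complete form to avoid an error of at most 2 points is a poor trade. Check the No assumption by imputing question 9 in the mice analysis.

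The cost is one or two sentences in the SAP and possibly a few more missing PainDETECT scores in the complete-case analysis. A limit of four reduces the noise but does not remove it, and it does not touch the question 9 understatement, which is why that needs its own check.
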